# 2.8 Exclusion Criteria

Exclusion criteria include: patients < 18 years of age; non-English speaking; not able to follow directions; inability to smell (anosmia); allergy to peppermint, spearmint, ginger and/or lavender; receiving bariatric surgery for gastroparesis; pregnant or breastfeeding; vulnerable subjects; receiving complementary therapy (healing touch, music therapy) or presently enrolled in another research study.

# 3 STUDY METHODS AND PROCEDURES

#### 3.1 Study Treatment/Intervention

Once consent is obtained, the licensed prescriber will enter an order into the patient's electronic medical record (EMR) for the aromatherapy product. It will be a one-time order to administer the aromatherapy product for complaints of nausea while on the surgical unit for the first 24 hours post-operatively. This order will appear on the medication administration record (MAR) in the EMR.

Pharmacy will review and release the aromatherapy order. Pharmacy will be provided with the study Subject Identification (SID) number, a copy of the patient's research consent and randomization scheme generated by SAS which will determine the protocol drug (aromatherapy product A or B). Pharmacy will apply a patient label to study drug and one label on the delivery sheet. The pharmacy will dispense the study drug to the Surgical Unit. The study drug will be placed in the patient's medication bin in the medication room closet to the patient's room. Pharmacy will maintain all delivery sheets in a secure location.

If the enrolled post-operative bariatric patient complains of nausea for first time (initial) while on the surgical unit within the first 24 hours post-operatively, the participant will be offered a one-time aromatherapy intervention with either product A or product B (based on the randomization scheme) for their nausea treatment. A member of the research team will instruct the patient on the use of the QueaseEASETM aromatherapy product (A or B) and also provide them with the educational handout (refer to appendix F: Aromatherapy patient education sheet). The instructions to use are the same for product A as product B.

The direct care nurse will assess the patient's nausea level prior to the intervention. The direct care nurse will provide the patient with their randomized product, and the patient can utilize the product for up to 5 minutes. The nurse will document this one time aromatherapy administration via the MAR. The nurse or a member of the research team will then reassess the patient's nausea level at 5 minutes.

After the aromatherapy intervention the nurse will remove and discard the patient label from the study drug and dispose of the study drug in the appropriate receptacle.

If the patient still complains of nausea following the one-time aromatherapy intervention with QueaseEASETM product A or product B, an antiemetic medication will be offered. The direct care nurse will complete the data collection form A (refer to appendix D: Data Collection Form A). The PI/SI will collect the completed data collection form A and store in a secure locked location. On day of discharge, a member of the research team will query the patients on the aromatherapy session using form B (refer to appendix E: Data Collection Form B). The PI/SI will collect and securely store the data collection form B once completed. A member of the research team will complete the demographic /outcomes sheet (refer to Appendix H: demographic/outcomes sheet) and the PI/SI will collect the completed demographic/outcomes sheet and store in a secure locked location.

Refer to Appendix I -- for tentative time table for this study.

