# 1.2 Hypothesis

(1) Patients using aromatherapy with the initial episode of nausea on the surgical unit will have a greater decrease in mean nausea levels compared to control group and (2) The use of aromatherapy will decrease the utilization of antiemetic medication in the first 24 hours for the post-operative bariatric patient population on the surgical unit.

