#### 1.3 Background and Significance

Inova Fair Oaks Hospital performs over 550 bariatric surgeries per year. These surgeries consist of laparoscopic sleeve gastrectomy and laparoscopic Roux-En-Y bypass. These patients receive general anesthesia and insufflation of gas in the peritoneal cavity for surgical visualization. According to Brown and colleagues (2018) general anesthesia causes an increased risk for post- operative nausea and vomiting (PONV) when compared with regional anesthesia. In addition, the nursing literature states that laparoscopic surgeries are associated with a higher incidence of PONV.

PONV occurs in one-third of post-operative patients (Ferruggiari, 2012; O'Malley 2016 & Stalling-Welden 2018). According to Adib-Hajbaghert and Hosseini, F. (2015) "patients who experience PONV describe it as one of the most stressful complications of surgery and prefer postoperative pain over it" (p. 827). PONV can result in discomfort, fluid and electrolyte imbalance, dehydration, increased blood pressure, strain on the surgical site, reduced patient satisfaction and delayed discharge (Abid-Hajbaghery, 2015; Brown, 2018; Hodge, 2014; Lee, 2017; O'Malley, 2016; Asay, 2018).

Traditionally, PONV is treated with the administration of antiemetic medications. However antiemetic medications have the following side effects: hypotension, dry mouth, excessive sedation, restlessness, fatigue, extrapyramidal reactions and limited dosing (Hodge, 2014; Adib-Hajbaghery, 2015; Karaman, 2019). Many patients would like the option of a non-pharmacological intervention for PONV. The American Society of Peri-Anesthesia Nurses (2006) developed clinical practice guidelines for the prevention and management of PONV. These guidelines cite aromatherapy as an intervention to consider for PONV in the post anesthesia care unit (Stalling-Welden, 2018). According, to O'Malley (2016) "aromatherapy provides an alternative therapy to manage nausea, one which is free of medication side effects and sedation" (p. 318).

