# 5 HUMAN SUBJECTS PROTECTION (RISKS, BENEFITS, AND ALTERNATIVES)

#### 5.1 Risks

Minimal risks, if any, are anticipated. Participants may experience dizziness, lightheadedness and/or headache.

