## 7 ADVERSE EVENT REPORTING

There are no known anticipated potential adverse events as a result of this study. However, any adverse events will be reported to the IRB. Protocol deviations will also be reported as required.

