# Aromatherapy and nausea level study on Surgical Unit for post-operative Inova Medical Group Bariatric Surgery

# Data Collection Form B

Did you use the QueaseEASE product?  If yes-  How beneficial was the aromatherapy?  O 1 2 3 4 5 maximal or very beneficial  Would you consider using QueaseEase™ in the future for nausea?  Yes/No  Would you recommend QueaseEase™ to family / friend?  Yes/No  Did participate experience any side effects from the product?  Yes/No  If yes, what was the side effect (s): Dizziness  Light-headedness  Headache  Other  Please provide any additional comments or feedback below:	TO ASK ON DAY OF DISCHARGE Aromatherapy (QueaseEase™) Questions: following questions:	: Research M	lember to a	sk the patient th	ie
How beneficial was the aromatherapy?  0 1 2 3 4 5 maximal or very beneficial  Would you consider using QueaseEase™ in the future for nausea? Yes/No  Would you recommend QueaseEase™ to family / friend? Yes/No  Did participate experience any side effects from the product? Yes/No  If yes, what was the side effect (s): Dizziness Light-headedness Headache Other	Did you use the QueaseEASE product?	Yes	No		
maximal or very beneficial  Would you consider using QueaseEase™ in the future for nausea? Yes/No  Would you recommend QueaseEase™ to family / friend? Yes/No  Did participate experience any side effects from the product? Yes/No  If yes, what was the side effect (s): Dizziness Light-headedness Headache Other	If yes-				
Would you recommend QueaseEase™ to family / friend? Yes/No  Did participate experience any side effects from the product? Yes/No  If yes, what was the side effect (s): Dizziness Light-headedness Headache Other	How beneficial was the aromatherapy?	2078	2 3 4	maximal or	
Did participate experience any side effects from the product?  Yes/No  If yes, what was the side effect (s): Dizziness Light-headedness Headache Other	Would you consider using QueaseEase™ in	the future fo	or nausea?	Yes/No	
If yes, what was the side effect (s): Dizziness Light-headedness Headache Othe	Would you recommend QueaseEase™ to fa	mily/friend	!?	Yes/No	
	Did participate experience any side effects i	from the proc	luct?	Yes/No	
Please provide any additional comments or feedback below:	If yes, what was the side effect (s): Dizzines	ss Light-h	eadedness	Headache	Other
	Please provide any additional comments or	r feedback be	elow:		

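### Side effects and perceived benefit of a 5-minute inhalation are first asked about on the day of discharge, after any rescue antiemetic, so an arm difference cannot be attributed to the inhaler itself

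*Combined protocol and SAP*

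**What the plan says.** Exposure is brief and happens once: under Section 3.1, "the patient can utilize the product for up to 5 minutes", and nausea is rated again at 5 minutes. Form A (Appendix D) records the 0-3 nausea level before and after, the product given, and whether an antiemetic was requested. It has no item on side effects or perceived benefit.

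Rescue comes next. Section 3.1 provides for it: "If the patient still complains of nausea following the one-time aromatherapy intervention", an antiemetic is offered. Section 3.2 also provides for an antiemetic in the control group. Section 1.2 expects use to differ by arm: "The use of aromatherapy will decrease the utilization of antiemetic medication in the first 24 hours".

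The product questions come last: "On day of discharge, a member of the research team will query the patients on the aromatherapy session using form B". Form B (Appendix E) has a 0-5 benefit rating and asks "Did participate experience any side effects from the product", listing dizziness, light-headedness, headache and other. It names the QueaseEASE brand for all patients, although Product B contains distilled water (Section 2.3).

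Two other places touch on harms. Appendix H has a side-effect item with no stated time, placed after the discharge date and not tied to the product. Section 7 sends adverse events to the IRB but sets no time for asking about them. Sections 5.1 and 7 also disagree: the first says "Participants may experience dizziness, lightheadedness and/or headache", the second "There are no known anticipated potential adverse events as a result of this study".

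**The concern.** Form B asks the patient what the inhaler did. By then the patient may have had one or more antiemetics, is further into recovery, and must recall a few minutes of inhalation. If hypothesis 2 is true, more control patients will have had antiemetics. Any symptom from those drugs that is put down to the inhaler raises the Product B side-effect rate. A real excess with Product A would then look smaller, and a harmless Product A could look better tolerated than water.

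The benefit rating has a similar problem, but its direction is less clear. A rescued patient may credit the inhaler with the drug's relief, or may mark it down because a drug was needed.

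At stake is the statement the investigators will probably want to make about tolerability of the inhaler. Once a patient has had rescue, no analysis can recover a report from before it. Adjusting for antiemetic use would condition on something that happened after randomization and is itself affected by the product.

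**Working it through.** **Sequence.** Nausea rating, inhalation of up to 5 minutes, second rating (Form A), antiemetic if needed, any further antiemetics within 24 hours (Appendix H has lines for several), then Form B on the day of discharge. No product-specific side-effect report is scheduled before rescue.

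**The plan's own figure.** The only rates in the plan are the nausea rates in Section 4.1: 80% in controls and a 20% reduction, two-sided 0.05, 90 per group. Read as 80% versus 60%, the usual formula gives

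n = [1.96√(2 × 0.70 × 0.30) + 0.8416√(0.80 × 0.20 + 0.60 × 0.40)]² / 0.20² = 82 per group,

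or 91 with continuity correction. Power at 90 per group is 0.839, so the plan's claim of at least 80% reproduces. Read as a relative reduction (80% versus 64%), n is 123 and power at 90 is 0.669. This point does not depend on the sample size. The rates are only borrowed below as stand-ins for rescue.

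**Assumptions, none from the documents.** Rescue r is 80% with Product B and 60% with Product A. A proportion q of rescued patients, 5% to 30%, has an antiemetic symptom and reports it as an effect of the inhaler. Product A itself causes side effects in a proportion a; Product B causes none.

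- Reported with Product A: 1 − (1 − a)(1 − 0.60q)
- Reported with Product B: 0.80q
- Shift when a = 0: (0.60 − 0.80)q = −0.20q
- Standard error of the difference when a = 0: √{[pA(1 − pA) + pB(1 − pB)]/90}

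| q | A, a = 0 | B | Shift (points) | SE (points) | Shift size / SE | Observed if true excess is 5 points |
|---|---|---|---|---|---|---|
| 5% | 3.0% | 4.0% | −1.0 | 2.7 | 0.4 | +3.9 |
| 10% | 6.0% | 8.0% | −2.0 | 3.8 | 0.5 | +2.7 |
| 20% | 12.0% | 16.0% | −4.0 | 5.2 | 0.8 | +0.4 |
| 30% | 18.0% | 24.0% | −6.0 | 6.1 | 1.0 | −1.9 |

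Example for the last column at q = 20%: 1 − 0.95 × 0.88 = 16.4%, less 16.0%, gives +0.4.

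With 64% rescue on Product A the shift is −0.16q, that is 0.8 to 4.8 points in size. If rescue does not differ by arm, the shift at a = 0 is zero.

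**Benefit rating.** If rescued patients credit b = 0.5 to 2 points of drug relief to the inhaler (assumed), the arm difference changes by (0.60 − 0.80)b = −0.1 to −0.4 on the 0-5 scale, or −0.08 to −0.32 with 64% rescue. If they mark the inhaler down instead, the sign reverses.

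**The case against.** The strongest reply is that nothing here is confounded. Rescue follows randomization and results from it, so the discharge comparison is a fair one of inhaler plus rescue as needed. That stands. A reader might infer that the Form B comparisons are invalid, and the documents do not support this. What is lost is attribution to the inhaler alone.

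Nor are the comparisons planned as such. Perceived benefit and side effects are not among the outcomes in Sections 3.4.1 and 3.4.2 or the tertiary outcome in the abstract. Only the general t-test and chi-square sentence in Section 4.2 could cover them. This stands and limits the weight of the point.

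A reader might also take Form B for the trial's only safety measure. It is not: Appendix H and Section 7 both capture side effects. Neither sets an earlier time, so they do not supply a report from before rescue. The consent form and patient education sheet were not available for this review and may ask patients to report effects at once.

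The mechanism is partly inferred. Section 1.3 says "antiemetic medications have the following side effects: hypotension, dry mouth, excessive sedation, restlessness, fatigue" and goes on to extrapyramidal reactions and limited dosing. It does not name dizziness, lightheadedness or headache. Hypotension and sedation make an overlap plausible, no more. Form B also asks specifically about the product, and the arithmetic takes every counted symptom to be misattributed.

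Last, the shift is small against the noise. At 90 per arm the 95% half-width in the table's scenarios runs from about 5 to 12 points (1.96 × SE), and fewer patients would widen it. The trial could not reliably resolve such an excess at either time. This stands too: the case for the change rests on getting the question right at little cost, not on a demonstrated large bias.

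**Conclusion.** The point holds in a limited form. The product-specific side-effect question and the benefit rating come only after antiemetics that the trial expects to differ by arm, and after a recall delay of unstated length. The answers can describe the whole strategy but cannot be attributed to the inhaler.

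For side effects the likely direction, if hypothesis 2 is true and drug symptoms are misattributed, is to mask harm from Product A. The illustrative size is 1 to 6 points, at or below about one standard error with 90 per arm, and it rests wholly on assumed rescue and side-effect rates. For benefit, the documents do not support a claim that the difference must shrink. The 5-minute nausea score precedes rescue, so it and the sample size are unaffected.

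This is a worthwhile data-collection improvement to descriptive items, not a threat to the primary result. The mismatch between Sections 5.1 and 7 is a separate wording matter.

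**What to change.** 1. Add Form B's yes/no side-effect question and its checklist to Form A at the 5-minute reassessment. Do not change when rescue is offered. Report the answers by arm as the tolerability measure attributable to the inhaler.
2. The 0-5 benefit rating may be added there too, but this is optional: the 5-minute nausea score already gives a benefit measure from before rescue.
3. Keep Form B and the Appendix H item at discharge for later effects and for the future-use and recommendation questions. Label them as measures of inhaler plus rescue, and present them beside the antiemetic use that Appendix H already records.
4. Replace the brand name on the patient questions with neutral wording such as 'the study inhaler'.
5. Separately, reconcile Section 7 with the three possible effects in Section 5.1.

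The cost is one short item on a form already in use, some wording edits, and about a minute more for a patient who may still be nauseated. There is also a blinding cost: Form A records Product A or B, and Section 2.3 says which is active, so the person taking the answers may know the allocation. Discharge collection is not clearly free of this, since Section 3.3 gives designated research team members access to the randomization scheme. Reading the checklist word for word would limit the effect. The sample size does not change.

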# 3.2 Control Group

Consented patients will be randomized into the control group and will receive aromatherapy product B. Pre and post nausea levels will be assessed and if the nausea level is not decreased an antiemetic will be administered as ordered.

#### 3.3 Randomization

Upon enrollment in the trial, each subject will be randomized to one of two treatment groups: Product A (aromatherapy inhaler product), Product B (Placebo product: inhaler with distilled water). Each product will look the same. SAS will be used to generate the randomization table using random numbers to determine which treatment subject #1 will receive; subject #2 will receive, etc., resulting in a total of 90 subjects for each treatment group. The randomization scheme will be located in a secured location in the pharmacy department and access will be granted to Pharmacy and designated research team members.

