#### **Study Methodology:**

Subjects will be provided with information about this research study by the following means: a member of the research team (IMG Nurse Practitioners) will discuss the research study during the patient's second pre-operative visit; study information will be uploaded to their MyChart portal; and flyers will be available in the IMG office (refer to appendix A: IMG office flyer). Interested patients will be able to fill out a brief form (refer to appendix B: Interested patient card) requesting to be contacted for further information, this form will be placed in a secure box at the reception desk or the patients can indicate interest by contacting one of the research team members. A member of the research team may need to access medical record information in order to confirm potential patient's phone number and or email address for further contact. A member of the research team will contact any interested patients and answer any questions regarding the research study. Consent will be obtained while the patient is in the peri-operative holding area on day of surgery by a member of the research team, excluding the IMG Nurse Practitioners. The research team member will determine if the patient is eligible for the study, discuss the study, answer any questions, and obtain consent (refer to appendix C: Consent). All members of the research team have completed Informed Consent Training. Once the consented post-operative bariatric patient complains of initial nausea on the Surgical Unit, the direct care nurse or research team member will ask the patient to rate their nausea level using a VAS on a 0-3 scale. Patients will be provided with either product A or B based on randomization scheme calculated by SAS (ver.9.4, Cary, NC). The patient will receive a one-time aromatherapy intervention. Nausea levels will be reassessed 5 minutes after the aromatherapy intervention. If the nausea level does not improve after the study drug intervention an antiemetic medication will be offered (refer to appendix D: Data Collection Form A).

On day of discharge a member of the research team will ask the patient the following questions regarding the Aromatherapy QueaseEASETM product (refer to appendix E: Data Collection Form B). The study will occur Monday through Thursday.

Did you use the QueaseEASE IM product?	Yes N	No	
If yes: How beneficial was the aromatherapy?	0 1 2 no benefit	3 4 5 very bene	eficial

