# Data Collection Form A

intervention	
Nausea level before aromatherapy:	0 1 2 3 No Nausea Some Alot Severe
Date:/ Time:	— , s
Administer Aromatherapy product/ Intervent	
Aromatherapy product given:	Product A Product B
Date:/ Time:	— 4
Reassess nausea level after aromatherapy:	
Nausea level 5 minutes after aromatherapy:	0 1 2 3 No Nausea Some Alot Severe
Date:/ Time:	- .a
Did the patient request an antiemetic after the are	omatherany intervention?
YES NO	omaticapy mes content.
Date:// Time:	W4
xx	_ ,
	Add Patient Label

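### Allocation list access reaches undefined research team members, and the A/B letter is recorded on forms collected by the role that obtains consent; both can be closed cheaply

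*Combined protocol and SAP*

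**What the plan says.** **List.** Section 3.3 describes a SAS table giving the treatment for subject 1, subject 2 and so on, 90 per group. The table is held in a secured pharmacy location, and "access will be granted to Pharmacy and designated research team members". The designated members are not identified.

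**Assignment.** Under section 3.1, "Pharmacy will be provided with the study Subject Identification (SID) number", together with the consent copy and the scheme. Then "Pharmacy will apply a patient label to study drug and one label on the delivery sheet", and it dispenses to the unit and keeps the delivery sheets.

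**Research team tasks.** Section 2.6 has all members work together to identify patients. The abstract's Study Methodology says: "The research team member will determine if the patient is eligible for the study, discuss the study, answer any questions, and obtain consent". Section 3.5 assigns consent to the PI or SI. For the 5-minute nausea level, section 3.1 says: "The nurse or a member of the research team will then reassess".

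**Letter.** Sections 2.3 and 3.3 fix A as the essential-oil inhaler and B as distilled water for every subject. Form A (Appendix D) has a field "Aromatherapy product given", with A or B to be marked, between the pre-treatment and 5-minute scores. Appendix H has the same choice on the sheet that holds the 24-hour antiemetic record. Form B has no such field. On completion, section 3.1 says "The direct care nurse will complete the data collection form A" and "A member of the research team will complete the demographic /outcomes sheet". It has the PI/SI collect both.

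**Blocks and blinding.** Section 4.1 gives 15 blocks of 12. Section 2.1 calls the trial single blind without saying who is blinded.

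**The concern.** Allocation concealment means that whoever decides on eligibility and takes consent cannot know or predict the next assignment. The plan leaves two avoidable routes to that knowledge.

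The first is the list itself. A designated member who also screens or consents on the day of surgery could read the next assignment beforehand, and nothing in the text prevents the overlap.

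The second is the letter. The code is fixed and the protocol prints its meaning, so a completed form carrying the letter discloses the arm to any reader who knows the key. Such forms pass to the PI/SI, who also obtain consent. In fixed blocks, past assignments carry information about the next one.

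What is at stake is mainly comparability of the arms at entry. There is a lesser risk at assessment: the primary end-point in section 3.4.1 is the change in a self-reported 0-3 score elicited by staff, and a scorer who knows the arm could influence it.

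**Working it through.** **1. Is each route needed, and is it closed elsewhere?**

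| Step | Who does it | Is list or letter needed? |
|---|---|---|
| Identify patients (2.6) | Research team | No |
| Eligibility and consent (Study Methodology; 3.5) | Research team member; PI or SI | No |
| Assign, label, dispense (3.1) | Pharmacy | Yes; Pharmacy holds the scheme |
| Give product, take 5-minute score (3.1) | Nurse gives; nurse or team member scores | No |
| Complete Form A / Appendix H (3.1) | Nurse / team member | Only because the forms ask for the letter |
| Collect both forms (3.1) | PI/SI | Sees the letter |

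The plan does separate some roles. The IMG Nurse Practitioners may not take consent (Study Methodology; 2.2), and approaching patients falls to members trained in consent (2.6). No comparable sentence covers list access. The inhalers look alike (3.3) and the only label described is a patient label (3.1), so the nurse can mark A or B only if the letter is carried to the bedside, where no described step uses it.

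**2. How far do past letters predict the next assignment?**

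Inputs: 15 blocks of 12, so 15 x 12 = 180 (4.1), and 90 per group (3.3). Assumptions: each block holds 6 A and 6 B (consistent with 90 per group but not stated), and the guesser knows the block size and boundaries.

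*Upper bound: every earlier letter seen at once.* For a block of 2m with m per arm, always guessing the arm with more places left gives

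expected correct = m + [2^(2m) / C(2m, m) - 1] / 2.

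With m = 6: 2^12 = 4096 and C(12, 6) = 924, so 4096/924 = 4.433, and 6 + (4.433 - 1)/2 = 7.716 of 12. That is 64.3%. Over 15 blocks it is 115.7 of 180, against 90 by chance. The assignments known with certainty average 2m/(m + 1) = 12/7 = 1.71 per block, which is 14.3%, or about 26 of 180.

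*Partial and delayed sight.* Let each earlier letter be seen with probability p, and the latest L patients not at all. With a A's and b B's seen in the block,

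P(correct) = max(6 - a, 6 - b) / (12 - a - b),

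averaged over the possible (a, b) and the 12 positions.

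| p | L | Correct | Of 180 | Certain |
|---|---|---|---|---|
| 1.0 | 0 | 64.3% | 115.7 | 14.3% |
| 0.8 | 0 | 59.8% | 107.6 | 3.7% |
| 0.9 | 2 | 57.3% | 103.1 | 1.2% |
| 0.8 | 2 | 56.5% | 101.7 | 0.6% |
| 0.8 | 3 | 55.3% | 99.5 | 0.2% |
| 0.6 | 3 | 54.2% | 97.6 | 0.03% |

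The values of p and L are assumptions. Sight would be incomplete because Form A arises only when a patient has nausea and uses the product, and forms arrive after the event. A delay of 2-3 patients with 60-90% seen gives 54-57%. At p = 0.8 the excess over chance is 101.7 - 90 = 11.7 or 99.5 - 90 = 9.5, so about 10-12 assignments in 180. By contrast, a person with the list knows all 180.

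**3. Does the change affect sample size?** No. It alters neither the 90 per group nor any assumption in section 4.1.

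**The case against.** The strongest reply is that every harm is conditional. The list is secured in pharmacy, access is confined to named parties, and the operating route runs through Pharmacy. A reader might infer that the list is open to the team, or that list holders do recruit, consent or score. The documents say neither. They only fail to exclude it.

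A reader might also infer that the letter on staff forms breaks the declared blinding, or that nurses are unblinded. That is not supported either. Single blind is compatible with staff knowing the arm, and no section reviewed gives direct care nurses the key. But single blinding does not excuse advance knowledge of the next assignment, because concealment is a separate safeguard.

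Scent is a further limit. Essential oils against distilled water may reveal the arm to patient and nurse whatever the paperwork shows, so removing the letter cannot fully protect the 5-minute score. This stands. Scent acts only during use, however, and has no bearing on enrolment.

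Two more points stand. The antiemetic entries on Appendix H are drug, dose and time, which leave an abstractor little discretion, and that sheet holds no nausea score. The opportunity at enrolment is also limited, because patients hear of the study and can register interest before the day of surgery.

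**Conclusion.** The point holds as a cheap improvement the sponsor should make. It is not a demonstrated failure. Two things are established from the text: list access extends to undefined team members with no stated separation from recruitment, consent or scoring, although assignment does not require it; and the role that obtains consent collects forms showing past assignments under a fixed, printed code.

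From past letters alone, predictability is at most about 64%, and about 54-57% with partial and delayed sight. Both figures rest on 6:6 blocks and a guesser who knows the block size and boundaries; the lower range also rests on the assumed p and L. The size of any resulting bias cannot be derived from the documents, and a claim that the nausea comparison is biased would go beyond them. The consent pages and some appendix pages were not available for review and could hold further detail on roles.

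**What to change.** - **Section 3.3:** limit list access to Pharmacy, and to the person who generates the list if that person does not recruit, consent, score or abstract outcomes.
- **Form A and Appendix H:** delete the Product A / Product B field.
- **Section 3.1:** keep the SID-to-product record with the delivery sheets that Pharmacy already retains, and do not send it to the unit. A separate kit number is not needed, and one placed on the patient label would be lost when the nurse discards that label after use.
- **Section 4.3.1:** merge allocation by PIN/SID at database lock, stating how the PIN on the forms links to the SID that Pharmacy holds.
- **Section 2.1:** as an accompanying clarification, say who is blinded.

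**Cost:** a few sentences and one field removed from each of two forms, with no extra patients. The product given would be verified from Pharmacy records rather than from the form. The documents do not name the list generator; if that person also recruits, consents, scores or abstracts, someone else must hold the list, which may matter in an unfunded study (section 8).
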